RATIONALE	Perioperative bleeding is a risk of cardiovascular implantable device insertion or replacement procedures. Bleeding complications predispose patients to interruption of OAC therapy, use of reversal agents, infection, and re-operation and prolong hospital stays. In patients with non valvular atrial fibrillation, interrupted Edoxaban therapy may offer safety and efficacy that is non inferior to continuous Warfarin therapy during these procedures
STUDY DESIGN	This is a prospective randomized comparative evaluation of Edoxaban and Warfarin for safety and efficacy in perioperative use in patients with non-valvular atrial fibrillation undergoing clinically indicated implantation or replacement of cardiovascular implantable electrical devices. This study is a randomized, open label, active-controlled trial with an open-label safety extension, designed to compare local and systemic bleeding within 30 days of cardiac rhythm device implant among patients randomized to continuous Warfarin or interrupted (<24 hours) Edoxaban. The study will have three phases; a run in phase to establish stable Warfarin therapy, an acute open label 30-day phase when patients will be randomized in a 1:1 ratio to receive interrupted Edoxaban or continuous Warfarin, which will be followed by an open label follow up phase for an additional 5 months for safety monitoring. Drug transitions will be performed according to approved drug labeling.
PRIMARY OBJECTIVE	The primary objective is to compare the rates of local and systemic bleeding in patients randomized to Edoxaban compared to patients randomized to continuous Warfarin in within 30 days of cardiac rhythm device implant with concomitant non-valvular AF.
SECONDARY OBJECTIVES	The secondary objectives are to compare the rates of thrombotic events (embolism or stroke) and MACE events through 6 months following the procedure in the Edoxaban and Warfarin groups.

NUMBER OF PATIENTS	A maximum of 400 patients will be enrolled
PATIENT SELECTION CRITERIA	
a) Patients with established AF and bradycardia on long term (>3 weeks) therapeutic OAC with Warfarin or another OAC who are undergoing new pacemaker system implant or existing pacemaker system revision.
 
b) Patients with newly detected bradycardia –tachycardia syndrome and AF who have been recently (less than 3 weeks) started on Warfarin, have a therapeutic INR and no thrombus on trans-esophageal echocardiogram (TEE) who are undergoing a new pacemaker system implant or revision.
 
c) Patients with AF and ventricular tachyarrhythmias (VT or VF) or acquired structural heart disease who are candidates for ICD therapy and are on long term (>3 weeks) therapeutic OAC with Warfarin or another OAC who are undergoing new ICD system implant or existing ICD system revision.
 
d) Patients with newly detected AF with VT or VF who have been recently (less than 3 weeks) started on Warfarin, have a therapeutic INR and no thrombus on TEE who are undergoing ICD system implant or revision
 
Exclusion Criteria:
 
a. Clinically significant valvular heart disease
 
b. Patients requiring CIED lead extraction e.g. for device site infection, endocarditis, leads under advisory or other conditions warranting lead(s) system extraction.
 
c. Recent (<1 month) myocardial infarction
 
d. Documented LA thrombus on TEE
 
e. Contraindications to anticoagulant therapy or adverse event with prior Warfarin or Edoxaban therapy
 
f. Creatinine clearance <30ml/min or >95 ml/min
 
g. Hepatic disease, advanced
 
h. Recent stroke (<3 months) or thromboembolic event
 
i. Recent (<3months) intracranial or other major bleeding event
 
j. Use of concomitant dual antiplatelet therapy or other oral, subcutaneous or parenteral anticoagulant therapy
 
k. Patients on Warfarin without therapeutic INR levels before study entry
 
l. Patients with other clinically significant medical condition

	
m. Patients with life expectancy < 1 year
 
n. Lead extraction procedures

TEST PRODUCT, DOSE, AND ROUTE OF ADMINISTRATION	
Edoxaban (30 mg tabs)
 
Edoxaban 60 mg orally daily dose for creatinine clearance 50 to 95 ml/min and Edoxaban 30 mg orally for creatinine clearance of 30 to 49 ml/min.

CONTROL PRODUCT, DOSE AND ROUTE OF ADMINISTRATION	Warfarin dose to maintain therapeutic INR, oral administration
DURATION OF PATIENT PARTICIPATION AND DURATION OF STUDY	
Screening: 7-26 days
 
Treatment: 5 days of randomized therapy prior to procedure (which is a single day)
 
Follow-up: 180 days

CONCOMITANT MEDICATIONS	Allowed as per approved FDA guidelines
EFFICACY EVALUATIONS	
PRIMARY ENDPOINT	Major local or systemic bleeding as defined in the protocol at 30 days after implant procedure
SECONDARY ENDPOINTS	The secondary objectives are to compare the rates of thrombotic events (embolism or stroke) through 6 months following the procedure in the Edoxaban and Warfarin groups and the rates of MACE events through 6 months following the procedure in the Edoxaban and Warfarin groups
OTHER EVALUATIONS	The exploratory objectives are to compare rates of hemoglobin reductions from pre-procedure to 24-48 hours post procedure in the Edoxaban and Warfarin groups
SAFETY EVALUATIONS	Safety monitoring during the study will be performed by an independent data monitoring committee (DMC), as well as medical and clinical monitors

	and the coordinating center. Sites will be monitored by a clinical monitor at least once during this short trial. Clinical sites will be required to report all procedure related complications, deaths and major adverse events to the medical monitor within 24 hours of learning of the event. All events will be adjudicated by an independent events committee.
PLANNED INTERIM ANALYSES	When approximately 200 subjects have completed the study through the 30-day visit, an interim analysis for safety will be conducted by an independent data monitoring committee. Serious adverse events will be monitored by the committee on an ongoing basis throughout the study. Based on the primary outcome in these 200 subjects, the study may continue to enroll up to 200 additional subjects, or be terminated.
STATISTICS Primary Analysis Plan	This study contains an internal pilot, and the primary endpoint will be evaluated when 200 patients have reached 30-days post procedure or withdrawn. Based on the primary outcome in these 200 patients, the study may enroll up to 200 additional subjects, or be terminated. Bleeding rates will be compared for non-inferiority using a 1-sided exact test (Primary Endpoint). If non-inferiority of Edoxaban is demonstrated, superiority will be assessed using a 2-sided exact test (Secondary Endpoint).
Rationale for Number of Patients	The study is designed based on a non-inferiority hypothesis, with an overall type I error rate of 0.025 (1-sided) with a non-inferiority margin of 1.5%.

LIST OF ABBREVIATIONS

AE	Adverse event
CIED	Cardiovascular Implantable Electrical Device
CRF	Case report form
DMC	Data Monitoring Committee
DSMB	Data Safety Monitoring Board
FDA	Food and Drug Administration
GCP	Good Clinical Practice
GFR	Glomerular Filtration Rate
HIPAA	Health Insurance Portability and Accountability Act of 1996
ICF	informed consent form
IEC	Independent Ethics Committee
IRB	Institutional Review Board
PI	Principal Investigator
SAE	Serious adverse experience

1. Background

Non-valvular (NV) atrial fibrillation (AF) frequently coexists with bradyarrhythmias and tachyarrhythmias.^(1,2) NVAF patients frequently have cardiovascular implantable electrical devices (CIEDs) implanted for symptomatic bradycardias or tachycardias. In the elderly population, 30-40% of all patients with bradyarrhythmias and pacemakers (PM) have concomitant AF. In patients receiving implantable cardioverter-defibrillators (ICDs), 15 to 20% can have concomitant AF. Thus, insertion or revision of CIEDs is common in NVAF patients and requires management of concomitant anticoagulant therapy. Warfarin is the most commonly used oral anticoagulant (OAC) and is either bridged or continued for the CIED procedure. Bridging requires hospital admission for intravenous heparin therapy in many patients and continuous Warfarin therapy is now being increasingly employed. However, this approach is associated with significant peri-procedural bleeding complications during and after CIED procedures.

In the BRUISE control study AF patients with PM or ICD devices were studied using two different regimens for peri-procedural anticoagulation. Birnie et al reported “clinically significant” device pocket hematomas in 3.5% of on Warfarin and in 16% of patients on heparin bridging therapy.⁽³⁾ In another multi-center study, 9.8% of patients on heparin or Warfarin had significant pocket hematomas after pacemaker implantation.⁽⁴⁾ This is in contrast to the general CIED population, in whom this complication was observed only in 0.2% of implanted individuals in a nationwide experience from Denmark.⁽⁵⁾ Kutinsky et al reported even higher rates of hematoma formation in the presence of clopidogrel and aspirin with continued Warfarin therapy ranging from 9.5 to 24%.⁽⁶⁾ Bleeding complications predispose patients to interruption of OAC therapy, use of reversal agents, infection, and re-operation and prolong hospital stays. Bridging therapy may be associated with increased embolic events due to varying anticoagulation status.⁽³⁾

In contrast, in the MOST study performed in patients with only sick sinus syndrome at entry, bleeding complications with pacemaker implantation were <0.4%.⁽⁷⁾ Dewland et al reported major complication rates with ICD implants in the National Cardiovascular Device registry. They noted device related complications of approximately 1% exclusive of major bleeding and hematomas with ICD implants.⁽⁸⁾

2. Purpose and Rationale

The rationale of this study is based on the long half-life of Edoxaban and its potential for reduced bleeding risk in comparison to Warfarin in patients with non-valvular AF. Continuous Warfarin therapy has been advocated to avoid the need for bridging anticoagulation at the time of elective surgical procedures such as CIED insertions or revisions. Bridging can increase bleed rates and prolong hospital stay. However, clinical studies show major bleeding complications in 43.5% of such patients in the perioperative period. (3) It is proposed that Edoxaban 60 mg when administered up to 18 to 24 hours before after the CIED procedure and resumed 12 to 24 hours after the procedure could potentially reduce this bleeding risk without loss of efficacy in stroke prevention.

In patients with non-valvular AF on OAC therapy with concomitant bradyarrhythmias or tachyarrhythmias warranting insertion or replacement of a CIED, an interrupted Edoxaban regimen without bridging anticoagulation is hypothesized to show comparable safety and efficacy to continuous Warfarin therapy for peri-procedural anticoagulation.

3. Objectives

3.1 Primary Objective

The primary objective is to compare the rates of bleeding (local or systemic) in patients randomized to Edoxaban compared to patients randomized to continuous Warfarin in within 30 days of cardiac rhythm device implant for non-valvular AF.

3.2 Secondary Objective

The secondary objectives are:

1. To compare the rates of thrombotic events (embolism or stroke) through 6 months following the procedure in the Edoxaban and Warfarin groups
2. To compare the rates of MACE events through 6 months following the procedure in the Edoxaban and Warfarin groups

MACE components include:

- Cardiovascular hospitalization
- Stroke

- Myocardial infarction
- Heart failure
- Vascular events
- Death

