4.1 Overview

This study is a randomized, open label, active-controlled trial with a safety extension (follow-up phase). It is designed to compare bleeding, local or systemic, within 30 days of cardiac rhythm device implant (acute phase) for non-valvular AF among patients randomized to continuous Warfarin or interrupted

Edoxaban. Randomization will be stratified by device type and HAS-BLED score (≤ 2 or ≥ 3). Patients will be randomized in a 1:1 ratio to receive interrupted Edoxaban or continuous Warfarin. This study contains an internal pilot opportunity to adjust the sample size or terminate the study, and there will be an interim analysis of the primary endpoint when 200 patients have reached 30-days post procedure or withdrawn. Based on the primary outcome in these 200 patients, the study may:

[figure not shown]
- Enroll 200 additional patients (pacemaker capped at 100 patients, ICD capped at 150 patients)
- Enroll 100 additional patients
- Be terminated

The study design is outlined in Figure 1.

Figure 1:

Study Design Flow Chart

Study Timeline

- Seamless design, enrollment does not stop between phases
-  Opportunity to stop if Part I objectives are not met
- Minimal resource commitment to Part II if Part I objectives not met
- For Part II, all sites enrolling, experience should lead to improved data quality compared to Part I
- Phases analyzed separately (primary) and combined

Eligible subjects must be stable on a therapeutic dose of Warfarin (INR 2-3) for three weeks prior to randomization. If potential patients are taking an anticoagulant besides Warfarin, or otherwise not meeting this criteria, must be switched to Warfarin and complete 3 weeks of dosing with INRs in the therapeutic range (run-in period) at randomization.

Comment [s1]: Segment into two sentences.
Insert period

Comment [s2]: delete

Comment [s3]: delete

Comment [s4]: Insert

The final INR should be performed on the day of randomization, and the procedure should be scheduled a minimum of 5 days and at most 15 days after randomization. Once eligibility has been confirmed and informed consent has been obtained, patients will be randomized via an interactive secure web randomization system. Patients will be randomized in a 1:1 ratio to Edoxaban or Warfarin. Randomization will be blocked by HAS-BLED score, and based on a randomization list, which will be created prior to commencement of the study.

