4.2 Justification of key elements of study design

4.2.1 Primary Endpoint

Peri-procedural bleeding and major local bleeding is of clinical concern for patients who require anticoagulation. Though catastrophic bleeding is rare, bleeding requiring clinical intervention is more frequent and can be studied in a modestly sized trial. Unlike strict use of change in hemoglobin, the need for intervention with vitamin K or blood products is recognizable to patients. Reduction in the need to administer an intervention for a procedural bleed should also result in lower health care resource utilization and costs.

Major local or systemic bleeding is defined as one of the following events:

- Significant hematoma requiring further surgery, resulting in prolongation of hospitalization, or requiring interruption of oral anticoagulation therapy
- Blood transfusion (permitted if hemoglobin is below 8 gm%, or 9 gm% in patients with active myocardial ischemia e.g. acute coronary syndrome)
- Surgical or interventional procedure to control bleeding that is symptomatic (shock, severe hypotension (90 mm hg systolic) or angina or myocardial infarction, which is not amenable to conservative measures (pressure dressing, ice packs) or volume expansion with intravenous fluids)
- Use of reversal agent injection to control bleeding leading to clinically manifest shock (e.g. hypotension requiring pressors, oliguria etc.) or death, severe and symptomatic hypotension (90 mm hg systolic or lower) or angina or hemoglobin decline to below 8 gm% not amenable to conservative measures (pressure dressing, ice packs or volume expansion with intravenous fluids)
- Hemorrhage leading to stroke or eventual fatality

(INR- guidelines for vitamin K injection or blood products will be established- see guideline below).

(aPTT or anti- factor Xa assay may or may not be available for Edoxaban to guide reversal – clinical and Hemoglobin guidelines as established above will be employed to guide use of reversal with blood products or transfusion).

Recommendations for Managing Elevated INRs or Bleeding in Patients Receiving VKAs

Condition	Suggested Intervention
INR less than 4.5 but above	Hold or reduce Warfarin dose. Resume Warfarin when INR is therapeutic.

therapeutic	

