4.2.4 Secondary endpoint evaluation

The secondary endpoint of superiority for peri-procedural bleeds will be assessed using the same methodology as the primary endpoint, except that the test will be for superiority. If the study does not meet the non-inferiority endpoint, superiority will not be assessed. The overarching goal is to reduce peri-procedural bleeds without causing an increase in stroke. Thrombi may form slowly though clinical presentation may occur months later. Considering events through 6 months post procedure helps to ensure that the interruption of Edoxaban for the procedure does not result in an increase in late-occurring thrombi or other safety issues.

5. Study Population

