6.1.2 Acute Open Label Phase

Subjects eligible for randomization will have maintained INR values in the therapeutic range based on a patient-specific dose of Warfarin – or baseline Warfarin therapeutic dose. From randomization to assessment of the primary endpoint, the study will be open label in design. In subjects randomized to Edoxaban in accordance with drug labeling, the transition from Warfarin and initiating Edoxaban should be performed when the INR has decreased below 2.5 after the discontinuation of Warfarin.

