6.1.3 Follow-up Open Label Phase

[figure not shown]
Subjects randomized to continuous Warfarin should have an INR in the first month, and continue monthly INRs as per standard practice guideline recommendations. Warfarin dosage should be adjusted according to standard practice to keep patients in the therapeutic range. Subjects randomized to Edoxaban should take it once daily per package dosing instructions (Edoxaban 60 mg daily dose for

creatinine clearance 50 to 95 ml/min and Edoxaban 30 mg for creatinine clearance of 30 to 49 ml/min). Subjects will be followed for an additional five months with a phone follow up at 3 months (± 1 week) and final follow up visit at 6 months (± 1 week). After the final follow up visit or after the subject is terminated from the study, subjects on Edoxaban transitioning to Warfarin should be maintained on Edoxaban until the INR is 2.0 or higher before Edoxaban discontinuation in accordance with drug labeling.

7. Study Visits

This study consists of three parts: a run-in or eligibility phase, an acute phase and a follow-up phase. Figure 2 for shows a diagram of study activities. Table 2 and Appendix A show visits.

Figure 2: Study events

Eligibility will be assessed when subjects have completed 3 weeks of Warfarin dosing. The procedure should be scheduled 5 to 15 days after randomization so that subjects are adequately anticoagulated with Warfarin or Edoxaban. The last dose of Edoxaban will be administered less than 24 hours prior to the procedure. Randomization will be obtained via IVRS once eligibility has been confirmed and the procedure has been scheduled.

On the day of the procedure, Warfarin will be continued and Edoxaban will be interrupted. Edoxaban dosing will resume a minimum of 16 and a maximum of 24 hours following the procedure. During and after the procedure, subjects will be assessed for safety and efficacy endpoints for bleeding and

embolism respectively as well as major adverse cardiovascular events (MACE). Edoxaban subjects will in general be discharged on the same day as the procedure, whereas Warfarin subjects will have their discharge timing determined on an individual basis by the investigator.

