8.1 Adverse events

An adverse event (AE) is the appearance or worsening of any undesirable sign, symptom, or medical condition occurring after randomization, regardless of the relationship to randomized treatment, procedures, underlying disease or comorbidities. All adverse events that occur or worsen after randomization should be reported on the CRF. When possible, the diagnosis or cause of the event should be reported instead of reporting symptoms. When multiple symptoms are related to a cause or diagnosis, only the cause or diagnosis should be reported.

Investigators should follow up with adverse events until they have resolved, the subject dies or withdraws from the study, or until the study is concluded.

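### Thrombotic and MACE endpoints are anchored to the procedure, although randomization and the Edoxaban arm's drug switch come 5 to 15 days earlier; stroke type is also left open

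*Combined protocol and SAP*

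**What the plan says.** **Window.** Section 3.2 states the thrombotic objective as "To compare the rates of thrombotic events (embolism or stroke) through 6 months following the procedure in the Edoxaban and Warfarin groups", and words the MACE objective over the same period. Section 7 says "During and after the procedure, subjects will be assessed for safety and efficacy endpoints for bleeding and" embolism, with MACE in the same sentence. Section 4.2.4 justifies the period by the procedural gap in dosing: "Considering events through 6 months post procedure helps to ensure that the interruption of Edoxaban for the procedure does not result in" more late thrombi or other safety problems.

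**Randomization and switch.** Section 4.1 requires that "the procedure should be scheduled a minimum of 5 days and at most 15 days after randomization", and Section 7 repeats the interval. All subjects enter on Warfarin. For those allocated to Edoxaban, Section 6.1.2 says that "initiating Edoxaban should be performed when the INR has decreased below 2.5 after the discontinuation of Warfarin". The synopsis describes five days of randomized therapy ahead of the procedure.

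**Analysis sets.** Section 10.5 evaluates primary and secondary endpoints in all randomized subjects. It says that randomization takes place on the procedure day, so that every randomized subject should receive a device. It limits the reporting of adverse events and other safety data to subjects whose implant was started. Section 10.4 summarizes binary secondary endpoints as percentages and per patient-year, without saying when follow-up begins.

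**Collection.** Section 8.1 defines an adverse event as one "medical condition occurring after randomization, regardless of the relationship to randomized treatment" and adds: "All adverse events that occur or worsen after randomization should be reported on the CRF".

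**Stroke type.** Section 3.2 does not qualify stroke. Section 4.2.1 lists "Hemorrhage leading to stroke or eventual fatality" as a major bleed, and Section 3.3 lists major intracranial hemorrhage as an exploratory event.

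**The concern.** The randomized comparison starts at randomization, and the Edoxaban strategy includes leaving Warfarin before surgery. If the thrombotic count starts at the procedure, it omits the one pre-operative period in which the protocol makes the arms differ. Under intention to treat, a subject with a stroke in that period stays in the denominator as event-free. The omission can depend on treatment, because only one arm switches.

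Section 4.2.4 sets the goal of fewer bleeds without more strokes. The thrombotic comparison is what supports the second half of that goal, so its numerator should hold every stroke or embolism that the allocated strategy could have caused.

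The undefined stroke type is a lesser worry of the same kind. If a hemorrhagic stroke on one arm can enter the thrombotic count, it can offset an ischemic stroke on the other and blur the signal that the endpoint is meant to detect.

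**Working it through.** **1. The plan's own figure.** The documents give no event rate, power or sample size for the thrombotic endpoint. The only stated size is for the bleeding endpoint (Section 10.2): rates 3.51% and 0.5%, margin 1.5%, one-sided 0.025, 300 patients, about 80% power.

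- Distance to the margin: 1.5% + (3.51% − 0.5%) = 4.51%.
- n per arm = (1.96 + 0.842)² × (0.0351 × 0.9649 + 0.005 × 0.995) / 0.0451² ≈ 150, so 300 in total.
- Power at 300 is 80.0% by the unpooled normal formula and 79.6% by the exact unconditional score test.

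The figure reproduces. It does not depend on how thrombotic events are counted.

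**2. Where a switch-period stroke goes, read as written.**

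| Event between randomization and procedure | Adverse event record (8.1) | Thrombotic/MACE endpoint (3.2, 7) | Safety report (10.5) |
|---|---|---|---|
| Implant still goes ahead | yes | outside | inside |
| Implant cancelled | yes | outside | outside |

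If randomization were on the procedure day, as Section 10.5 assumes, nothing would be lost. Sections 4.1 and 7 contradict that assumption, and the switch in Section 6.1.2 needs time between randomization and surgery. Appendix B also shows that not everyone randomized has a procedure: in the continuous-Warfarin source data, 8 of 343 (2.3%) did not. At that rate, 150 per arm would include 150 × 8/343 = 3.5 such subjects.

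**3. Length of the interval** (5 to 15 days; 180 days of follow-up from the synopsis).

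- Share of time from randomization to day 180: 5/185 = 2.7%; 15/195 = 7.7%.
- Patient-years in 150 Edoxaban patients: 150 × 5/365 = 2.1; 150 × 15/365 = 6.2.

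**4. Expected strokes.** The documents give no stroke rate. I assume a constant 1% to 4% per year; expected count = n × rate × days/365.

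| n per arm | 180 days after procedure | 5-day interval | 15-day interval |
|---|---|---|---|
| 150 | 0.7 to 3.0 | 0.02 to 0.08 | 0.06 to 0.25 |
| 200 | 1.0 to 3.9 | 0.03 to 0.11 | 0.08 to 0.33 |

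A constant rate may understate risk during a drug change; the documents offer nothing to test that.

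**5. Stroke type.** Sections 3.2 and 4.2.1 together allow a hemorrhagic stroke within 30 days to meet both the thrombotic and the primary bleeding endpoint. From day 31 to 6 months it could meet only the thrombotic one, because the primary endpoint has closed. No passage says that it should count as thrombotic, and none says that it should not.

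**The case against.** Section 3.2 fixes only the end of the window. The sentence in Section 7 is a visit narrative, not a counting rule. Secondary endpoints are evaluated in all randomized subjects, adverse events are recorded from randomization, and both visit tables mark adverse events in the pre-procedure column. A procedure-anchored window also fits a question about peri-procedural anticoagulation. This stands in part: the start is implied, not stated, and the events are collected. But recording an event does not carry it into the comparison, and no passage places a pre-procedure stroke in the endpoint.

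The lead-in is there so that patients are adequately anticoagulated, and nothing in the switch instruction requires an unprotected gap. That stands. The documents give no evidence that the switch causes strokes; the argument for counting is that the interval is randomized exposure.

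The expected loss is a fraction of an event, and any sparse endpoint can turn on one event. That stands too, and limits the weight of the point.

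On stroke type, the endpoint is headed as thrombotic, hemorrhage is named under bleeding, the synopsis sends all events to adjudication, and the goal in Section 4.2.4 speaks of stroke without qualification. One event may also properly contribute to two endpoints analysed separately. These points rule out any claim that double counting is prescribed. They do not supply a definition: Section 4.2.3 has the committee check potential primary events against the study definition, and for thrombotic stroke there is none to apply.

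Section 10.4 leaves further analysis detail to a later SAP, which could settle both matters. The endpoint's time origin is better fixed in the protocol text that defines it.

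**Conclusion.** The point holds as a should-fix matter of endpoint definition. As worded, the thrombotic and MACE comparisons start at the procedure while the intention-to-treat population starts 5 to 15 days earlier, and the interval between holds a drug change in one arm only. It is 2.7% to 7.7% of randomized time to day 180. Expected strokes in it are 0.02 to 0.25 per 150-patient arm, resting on an assumed constant 1% to 4% per year. The primary sample size and power are untouched.

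Two stronger readings are tempting. A reader might infer that the plan discards strokes during the switch. It does not: they are recorded as adverse events, and where the implant goes ahead they appear in the safety report. The firm gap is their absence from the secondary comparison as worded, plus their absence from the safety report when the implant is cancelled. A reader might also infer that every hemorrhagic stroke is scored twice. The documents do not say so. They leave the assignment open, and any overlap with the primary endpoint is confined to 30 days.

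**What to change.** - In Sections 3.2, 7 and 10.4, count thrombotic and MACE events, and patient-years, from randomization through 6 months after the procedure, for all randomized subjects. Give subjects who have no procedure an equivalent fixed end date. Since Section 7 has the procedure scheduled before randomization, 6 months from the scheduled date would serve.
- Reconcile Section 10.5 with Sections 4.1 and 7 on when randomization takes place, and make sure that events in randomized subjects whose implant was never started are reported.
- Define the thrombotic endpoint as ischemic stroke or systemic embolism. Report hemorrhagic stroke separately through 6 months and within MACE. Assigning it to the primary bleeding endpoint alone would not do, because that endpoint ends at day 30 and later hemorrhagic strokes would leave both comparisons.

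Cost: wording, a stroke-type field on the MACE form, one extra table, and follow-up of the few subjects who have no procedure. The pre-procedure events themselves are already collected under Section 8.1. Few events will be added, so the gain is a complete and interpretable comparison rather than more precision.
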